TIPN manifests via several different pathophysiological mechanisms that can be assessed by current modalities; none of which have yet emerged as a widely-adopted standardized approach. Taxane disruption of microtubules impairs the normal self-maintenance of neurons which is evident structurally as the degeneration of distal axons and nerve terminals. Inflammatory changes occur as the innate immune system responds to these damaged and leaking organelles. Genetic polymorphisms in neuronal and inflammatory cells contribute to individual variability in TIPN vulnerability. Functionally, as a neuronal myelin sheath deteriorates it increases the membrane surface area through which current must flow, slowing electrical conduction velocity and weakening its signal amplitude. Finally, as a result of the above mechanisms, degradation and inflammation can alter large peripheral nerves to the point that gross anatomic changes are evident on imaging.

Ultrasound (US) is a non-invasive, non-irradiating, emerging imaging modality which can be used to assess peripheral nerves. Nerve fiber cross-sectional area (CSA), echogenicity, and vascularity are assessed and provide an indication of nerve health and potential pathology. The majority of US data have been published on detection of entrapment syndromes such as carpal tunnel syndrome. In these cases the most common US findings include nerve enlargement, decreased echogenicity proximal to the entrapment, and an increase in nerve vascularity.⁷ Other studies have found that US can detect other peripheral nerve lesions or neuropathies, with the most reliable finding a change in nerve CSA. Ultrasound measurements of the sensory sural nerve at the distal calf in healthy participants without neuropathy had an average CSA of 5.3 mm² with standard deviation 1.8 mm² for a normal reference range of 1.7-8.9 mm².⁸ Another ultrasound study assessed the sural nerve more distally at the ankle and found a smaller CSA which was significantly enlarged ($p < 0.001$) in patients with diabetic

A Pilot Study Using Ultrasound for the Detection of Taxane-Induced Peripheral Neuropathy
Wake Forest Baptist Comprehensive Cancer Center (WFBCCC)
CCCWFU # 97217

polyneuropathy as compared to healthy controls (mean/standard deviation 2.59 / 0.96 mm² as compared to 1.40 / 0.59 mm²).⁹

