To date, there has only been one small study assessing US detection of chemotherapy-induced peripheral neuropathy; this was done among colorectal cancer patients who had received oxaliplatin. Similar to several other etiologies of nerve lesions/neuropathies, this study also found an increased peripheral nerve CSA compared to reference values. Interestingly, although the patients had denied symptoms of neuropathies at time of recruitment, this study found areas of increased peripheral nerve CSA at upper extremity sites of entrapment such as the carpal tunnel and ulnar groove; it did not find US abnormalities in terms of CSA or echogenicity at the sural nerve or other sites.¹⁰ Oxaliplatin has a much different mechanism of action from the taxanes; as a platinum-based agent it causes DNA cross-linking which inhibits cancer cell growth. Oxaliplatin-induced neuropathy is also a distinct entity that is characterized by cold sensitivity and mediated by prolonged opening of sodium ion channels along neuronal axons.¹¹ On a review of publications in the MEDLINE database as well as abstracts from the American Society of Clinical Oncology, we did not find any other prior studies that focused on the use of US to detect chemotherapy-induced peripheral neuropathy, and none for TIPN.

As noted above, there are currently several different diagnostic modalities that can assess TIPN, including self-reported symptoms, physical examination, nerve conduction study, sudometer testing, and skin biopsies. But each have limitations so that none have emerged as a widely-adopted standardized approach.

In routine practice, most clinicians rely on patients' self-reported symptoms alone for TIPN detection. These symptoms can be measured on one of several clinician-administered grading scales, although these have inter-scale and inter-observer variability.¹² The European Organization for Research and Treatment of Cancer (EORTC) QLQ-CIPN20 Questionnaire is a 20-item self-reported survey that is easy to administer and was validated across participants in four large cooperative group trials.¹³ Furthermore, although in many patients the development of acute TIPN symptoms is predictive of eventual chronic TIPN,¹⁴ some patients develop a disproportionately delayed TIPN that is not able to be self-reported early enough to allow for intervention.

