5.4.6 Use of analgesics or treatments for neuropathy

5.4.7 History of clinically documented compressive neuropathy (carpal tunnel syndrome)

6.0 Analytic Plan

6.1 Sample Size and Power

6.1.1 Primary outcome:

This current study will enroll a sample size of 22 in TIPN patients to compare to historical data that was previously collected from 60 healthy patients. Using a two-sided test and significance level of 0.05, we will have an 80% power to detect an effect size of 0.73 (unit: standard deviation [SD]) when comparing TIPN patients to that historical data. We have permission to utilize historical data (primary data) collected from healthy patients which found that the mean and SD of the tibial nerve CSA were 14.2 and 4.4 mm², respectively (published by Cartwright et al., 2008). Assuming the same SD in TIPN patients, we will have more than 80% power to detect a difference of 3.2 mm² for the tibial nerve. Based on Riazi et al. (2012),³² the mean increase in size of tibial nerve was 5.3 when comparing subjects with diabetic sensorimotor polyneuropathy and control subjects. Even though the study sample is not exactly the same, with the minimal detectable difference equal to 3.2, we should have sufficient power for this analysis.

6.1.2 Secondary outcome:

In historical data collected from healthy patients (Cartwright et al., 2008),⁸ the mean and standard deviation (SD) of the sural nerve CSA were 5.3 and 1.8 mm², respectively. Assuming the same SDs in TIPN patients, we will have more than

80% power to detect a detectable difference of 1.3 mm² for the sural nerve between TIPN patients and healthy patients.

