6.2 Analysis of Primary Outcome

The distribution of the primary outcome, nerve CSA, will be transformed to satisfy conditional normality assumption if necessary. It will be compared to the historical data from healthy patients using two-sample t-test (two-sample t-test selected as primary data from the historical control patients is available and will be used for analysis). We will also compare the nerve CSA in our study sample to that in the historical diabetic neuropathy patients and historical oxaliplatin neuropathy patients using one-sample t-test. The general linear model will be used to evaluate any factors (e.g., age) that may be associated with the nerve CSA. Due to the limited sample size, no more than two covariates will be included in the model.

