6.3 Analysis of Secondary Outcome

The analysis of sural sensory nerve CSA will be the same as that specified for primary outcome. To examine the associations between nerve CSA and NCS measures, the self-reported neuropathy scale, and intraepidermal nerve fiber density, Spearman's rank correlation coefficient will be used. The general linear model will be also used to evaluate the association after adjusting for one or two risk factors (e.g., age). Nerve CSA will be treated as the dependent variable. NCS measures, the self-reported neuropathy scale, and intraepidermal nerve fiber density are the covariates of interest. They will be fitted in the model one at a time.

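### Comparisons with historical diabetic and oxaliplatin patients use a one-sample t-test, which ignores the sampling error of the historical means and overstates significance

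*Combined protocol and SAP*

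**What the plan says.** Section 6.2 sets out two kinds of comparison for nerve CSA. Against healthy adults the test is two-sample, and the plan gives its reason: "two-sample t-test selected as primary data from the historical control patients is available". Against other neuropathies, the 22 TIPN patients are compared with "historical diabetic neuropathy patients and historical oxaliplatin neuropathy patients using one-sample t-test".

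The same section says that CSA "will be transformed to satisfy conditional normality assumption if necessary". Section 6.3 extends all of this to the second nerve: "The analysis of sural sensory nerve CSA will be the same as that specified for primary outcome". There are therefore up to four one-sample comparisons (two reference groups, two nerves).

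The documents say little about the reference groups:
- **Diabetic, sural nerve at the ankle** (section 1.0): "mean/standard deviation 2.59 / 0.96" mm², with no number of patients.
- **Diabetic, tibial nerve** (section 6.1.1): only that "the mean increase in size of tibial nerve was 5.3" relative to controls, with no group mean, SD or number.
- **Oxaliplatin** (section 1.0): "there has only been one small study assessing US detection of chemotherapy-induced peripheral neuropathy", with no CSA mean, SD or number.

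**The concern.** The wording compares two groups of patients. It does not test TIPN against a fixed clinical threshold. A one-sample t-test allows for the sampling error of the 22 TIPN patients and sets that of the historical mean to zero. The historical mean comes from a finite sample, so the standard error is too small and the test rejects too often.

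The reason given for the two-sample test against healthy adults suggests that the one-sample test was chosen for the other groups because their individual records are not available. That does not follow, because a two-sample t-test needs only the mean, SD and n of each group.

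A p-value just under 0.05 could be read as showing that nerves in TIPN differ in size from those in diabetic or oxaliplatin neuropathy when the evidence is weaker than stated. These are the plan's only comparisons of TIPN with other neuropathies.

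**Working it through.** The plan gives no error rate or power for the one-sample comparisons, so there is no figure of its own to reproduce here.

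**Inputs**
- TIPN sample size: 22 (section 6.1.1).
- Level: two-sided 0.05, stated in 6.1.1 for the primary test and assumed here for the supplementary ones.
- TIPN sural SD: 1.8 mm². Section 6.1.2 reports that in healthy adults the mean and "standard deviation (SD) of the sural nerve CSA were 5.3 and 1.8" mm², and assumes the same SD in TIPN.
- Diabetic sural SD: 0.96 mm² (section 1.0).
- Historical sample size m: not given; assumed 10, 15, 30, 60 or 100.
- SD ratio r = historical SD / TIPN SD: assumed 0.53, 1 or 1.5. The first is 0.96/1.8 = 0.533. It is illustrative only, because the two SDs come from different sites on the leg (ankle and distal calf).

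**Formula.** Let s be the TIPN SD. The one-sample test uses the standard error s/√22. The correct one is √(s²/22 + r²s²/m), which is larger by

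f = √(1 + 22r²/m).

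With normal data and equal true means, the one-sample statistic is exactly f times a t variable on 21 degrees of freedom. The critical value is 2.0796, so

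true type I error = P(|t₂₁| > 2.0796/f).

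For example, r = 1 and m = 30 give f = √(1 + 22/30) = 1.317, 2.0796/1.317 = 1.580, and P(|t₂₁| > 1.580) = 12.9%.

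**True type I error of the nominal 5% test**

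| r | m = 10 | 15 | 30 | 60 | 100 |
|---|---|---|---|---|---|
| 0.53 | 11.8% | 9.5% | 7.2% | 6.1% | 5.7% |
| 1 | 25.8% | 20.0% | 12.9% | 9.0% | 7.4% |
| 1.5 | 40.4% | 32.7% | 21.5% | 13.9% | 10.4% |

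From m = 10 to m = 100, f falls from 1.275 to 1.031 (r = 0.53), 1.789 to 1.105 (r = 1) and 2.439 to 1.223 (r = 1.5). Simulation with 400,000 runs per setting agrees with these rates. In the same 15 settings Welch's test rejects in 4.96% to 5.15%.

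**Effect on one result.** With a TIPN SD of 1.8 mm², the difference that gives a one-sample p of 0.050 is 2.0796 × 1.8/√22 = 0.80 mm². Welch's test on the same difference gives:

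| Reference SD (mm²) | m = 10 | 15 | 30 | 60 | 100 |
|---|---|---|---|---|---|
| 0.96 | 0.114 | 0.090 | 0.068 | 0.059 | 0.055 |
| 1.8 | 0.261 | 0.195 | 0.121 | 0.083 | 0.069 |

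**The case against.** **Low stakes.** No objective or listed outcome rests on these tests. Sections 2 and 5 deal with TIPN against healthy adults and with correlations within TIPN. The diabetic and oxaliplatin comparisons take up one sentence in 6.2, with no hypothesis, power calculation or decision attached, in a 22-patient pilot. This stands, and it limits the importance of the point. It does not make a prespecified test valid.

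**Unknown size.** The documents give m for neither group, so the error could be negligible or severe, and only the oxaliplatin source is called small. This also stands. It affects the size, not the direction: f exceeds 1 for every finite m.

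**Mixed sites.** The ratio 0.53 sets an ankle SD against a distal-calf SD, while section 4.6 says the sural nerve is measured at the ankle. The criticism is fair, and the ratio should be read only as an illustration. Section 1.0 also gives a same-site pair, 0.96 in diabetic patients and 0.59 in healthy controls. If TIPN had the healthy SD at that site, r would be 0.96/0.59 = 1.63. At m = 60, f is then 1.404 and the error P(|t₂₁| > 1.481) = 15.3%. The better-matched pair makes matters worse.

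**Welch is not always larger.** For very large differences Welch's extra degrees of freedom can give the smaller p. At a one-sample t of 8 with r = 0.53 and m = 30, the values are 8.2e-8 (one-sample) and 4.4e-8 (Welch). This is correct but has no bearing near 0.05. The claim here is about how often the one-sample test rejects when the true means are equal, and that is too often for every finite m.

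**A fixed reference value.** A one-sample test is valid if the hypothesis is restated as a comparison with a fixed constant. Section 6.2 does not say that; it compares patients with patients.

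**Conclusion.** The concern holds. As written, the comparisons with diabetic and oxaliplatin patients leave out the sampling error of the historical means, and their p-values overstate the evidence.

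The direction is certain. The size rests on assumed m and r and on normal data: the excess is small if the historical group is large or less variable than the TIPN group, and serious if it is small or more variable. The primary tibial and secondary sural comparisons with healthy controls are two-sample and are not affected. The change should be made, but it does not touch the trial's main conclusions.

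**What to change.** In section 6.2, and so in 6.3:
- Replace the one-sample t-test with Welch's two-sample t-test from summary statistics (TIPN mean, SD and n; published mean, SD and n). Do not use a pooled-variance test: it can err in the opposite direction when the historical group is larger and less variable.
- Run it on the untransformed CSA scale, even if the healthy-control analysis is transformed, because a published raw-scale mean cannot serve as the reference for transformed data.
- Report the difference with its 95% confidence interval, and name the source used for each comparison.
- Where a source gives no mean, SD or n for the same nerve and site, report the comparison descriptively without a p-value.
- State that Welch's test corrects the standard error but not bias from differences in measurement site or study.

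The cost is two or three sentences and no new data collection. The p-values become less favourable. Some of the four comparisons may end up descriptive only. On the documents' own figures, three lack mean, SD and n (diabetic tibial and both oxaliplatin) and the fourth (diabetic sural) lacks n, so the cited papers must be checked first.

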6.3 Analysis of Secondary Outcome

The analysis of sural sensory nerve CSA will be the same as that specified for primary outcome. To examine the associations between nerve CSA and NCS measures, the self-reported neuropathy scale, and intraepidermal nerve fiber density, Spearman's rank correlation coefficient will be used. The general linear model will be also used to evaluate the association after adjusting for one or two risk factors (e.g., age). Nerve CSA will be treated as the dependent variable. NCS measures, the self-reported neuropathy scale, and intraepidermal nerve fiber density are the covariates of interest. They will be fitted in the model one at a time.

6.4 Analyses of Exploratory Outcomes

Spearman's rank correlation coefficient will be used to assess the associations between activated mast cells in skin biopsies, serum inflammatory markers, severity of symptoms, and primary outcome and secondary outcomes in TIPN patients.

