2.3 Exploratory Objectives

2.3.1 To assess activated mast cells in skin biopsies in TIPN patients in relation to severity of symptoms and above findings.

2.3.2 To assess serum inflammatory markers in TIPN patients in relation to severity of symptoms and above findings.

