3.1 Inclusion Criteria

- Breast cancer (any stage).
- Previously or currently receiving taxane-based chemotherapy.
- Clinical symptoms of peripheral neuropathy noted in medical record and suspected to be secondary to taxane-based therapy.
- Ability and willingness to understand and sign an informed consent.

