4.5 Clinical assessment (Encounter 2)

Clinical assessment will take place in the CCC outpatient clinic and will include a focused history by one of the study investigators or research employees. The medical

A Pilot Study Using Ultrasound for the Detection of Taxane-Induced Peripheral Neuropathy
Wake Forest Baptist Comprehensive Cancer Center (WFBCCC)
CCCWFU # 97217

record will also be reviewed to confirm details of the medical history. The focused history will assess age, body-mass index (BMI), breast cancer staging, types and dosages of chemotherapy received, corticosteroid and analgesic use, and presence of comorbidities (diabetes, B12 deficiency, thyroid disorders, alcoholism, depression, carpal tunnel syndrome, sciatica). . A physical examination will occur to document strength and reflexes. The QLQ-CIPN20 questionnaire will also be administered at this encounter.

In most cases, blood testing will be added on to regularly scheduled phlebotomy for clinical labs which are drawn as part of routine oncology care. Some participants may require an additional blood draw if insufficient blood samples were collected. For the purposes of our study, 12mL of venous blood will be collected in a sodium heparin (green-top) collection tube and then transferred directly to [name] lab for processing.

Blood Sample Preparation

1. Email notification will be sent to [name] ([contact]), [name] ([contact]) and [name] ([contact]) the day before the blood collection.
2. Blood will be collected in two green-top vacutainer tubes containing heparin (60 USP Units of Lithium Heparin/6ml tube), and immediately inverted 8-10 times to prevent coagulation.
Attention: Protocol #: CCCWFU # (97217) and the ORIS PID in addition to the other standard information should be on the tube.
3. Samples will then be transported from the Cancer Center to the [name] lab (Lab: [name], [name], Office: [name]).

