5.4 Covariates

5.4.1 BMI

5.4.2 Age

5.4.3 Breast cancer staging

5.4.4 Types/dosages of chemotherapy and corticosteroids received

5.4.5 Presence of previously documented comorbidities (diabetes, B12 deficiency, thyroid disorders, alcoholism, depression, carpal tunnel syndrome, sciatica)

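### The unadjusted Spearman correlations in Section 6.4 pool currently and previously taxane-treated patients, so a marker–symptom correlation cannot be read as a link within treatment phase

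*Combined protocol and SAP*

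**What the plan says.** - **Who is pooled.** Section 3.1 admits women "Previously or currently receiving taxane-based chemotherapy". It sets no limit on time since the last dose.
- **When samples are taken.** Section 4.5 says that in most cases "blood testing will be added on to regularly scheduled phlebotomy for clinical labs which are drawn as part of routine oncology care". The Section 4.2 calendar fixes two things: consent comes first, and blood and the QLQ-CIPN20 share a day. Other tasks, including biopsy, may fall at any clinical encounter. No sample is tied to the taxane schedule.
- **What is asked.** Section 2.3 has two exploratory objectives: "To assess activated mast cells in skin biopsies in TIPN patients in relation to severity of symptoms and above findings" (2.3.1) and "To assess serum inflammatory markers in TIPN patients in relation to severity of symptoms and above findings" (2.3.2).
- **How it is analysed.** Section 6.4 is one sentence: Spearman's coefficient is used to "assess the associations between activated mast cells in skin biopsies, serum inflammatory markers, severity of symptoms" and the primary and secondary outcomes. It names no covariate, stratum or significance level.
- **Adjustment elsewhere.** Section 6.3 says "The general linear model will be also used to evaluate the association after adjusting for one or two risk factors (e.g., age"). That model has nerve CSA as the dependent variable, so it does not reach marker–symptom links.
- **Covariates.** Section 5.4.4 lists "Types/dosages of chemotherapy and corticosteroids received". Neither treatment phase nor time since last taxane is listed, and no covariate is assigned to Section 6.4.
- **Data available.** Appendix D records start and stop dates of the most recent taxane. Appendix E has the blood-sample date and Appendix G the biopsy date.

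**The concern.** A patient sampled between cycles and one sampled long after her last dose enter the same rank correlation. If being on treatment moves both a marker and the past-week symptom score, the two phases form two clouds. The pooled coefficient then mixes the distance between the clouds with any association inside them. Shifts in the same direction can produce a correlation where none exists within phase, and opposite shifts can hide one that does.

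The same-day rule for blood and questionnaire does not prevent this. It ensures that both values come from the same phase, which is the condition under which a phase effect on both appears as a correlation. Biopsy-based mast cell counts lack even the same-day rule.

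At stake is what a reader may conclude from objectives 2.3.1 and 2.3.2: that a marker tracks severity, or only that it tracks who is still on chemotherapy.

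**Working it through.** Section 6.4 states no sample size, power or effect size, so there is no figure to reproduce.

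**Inputs from the protocol.** n = 22 (Section 6.1.1). Two-sided 0.05 is stated there for the primary outcome and is borrowed here. At most two covariates are allowed (Section 6.2).

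**Assumed inputs.** Patients on treatment: 11 or 6 of 22. Phase shifts: 0.5 to 1.5 within-phase SD. The documents give neither.

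**Large-sample formula.** Let p be the proportion on treatment, dx and dy the phase shifts in marker and severity, and ρ the within-phase correlation. With v = p(1 − p), the pooled (Pearson) correlation is

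r = (ρ + v·dx·dy) / √[(1 + v·dx²)(1 + v·dy²)].

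At p = 0.5, v = 0.25:
- ρ = 0, both shifts 0.5: 0.0625/1.0625 = 0.06
- ρ = 0, both shifts 1: 0.25/1.25 = 0.20
- ρ = 0, both shifts 1.5: 0.5625/1.5625 = 0.36
- ρ = 0.5, shifts +1 and −1: (0.5 − 0.25)/1.25 = 0.20

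**Simulation at n = 22.** Normal variables, 40,000 runs per setting. Spearman is tested by t on 20 df. Partial Spearman uses rank residuals on phase and is tested on 19 df.

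*No within-phase link, equal same-direction shifts:*

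| Shift (SD) | On treatment | Mean pooled rho | Positive, unadjusted | Positive, adjusted |
|---|---|---|---|---|
| 0.5 | 11 | 0.06 | 5.6% | 4.9% |
| 0.5 | 6 | 0.05 | 5.5% | 5.0% |
| 1 | 11 | 0.20 | 15.4% | 5.0% |
| 1 | 6 | 0.16 | 11.1% | 5.2% |
| 1.5 | 11 | 0.38 | 43.5% | 4.9% |
| 1.5 | 6 | 0.30 | 28.0% | 5.5% |

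*True within-phase correlation 0.5:*

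| Shifts (SD) | On treatment | Mean pooled rho | Power, unadjusted | Power, adjusted |
|---|---|---|---|---|
| none | 11 | 0.46 | 62% | 60% |
| +0.5, −0.5 | 11 | 0.37 | 43% | 59% |
| +0.5, −0.5 | 6 | 0.39 | 46% | 59% |
| +1, −1 | 11 | 0.15 | 10% | 58% |
| +1, −1 | 6 | 0.21 | 15% | 58% |

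**Where the effect is small.** Both variables must shift. At an even split with the marker shifted 1 SD, a severity shift of 0, 0.25 or 0.5 SD gives 5.1%, 5.6% or 7.8% positives. With 4 of 22 on treatment and both variables shifted 1 SD, the rate is about 8%.

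**Cost of adjusting.** If phase has no effect, power at ρ = 0.5 goes from 62% to 60%. The correlation detectable with 80% power is tanh[(1.96 + 0.84)·√(1.06/19)] = 0.58 unadjusted, and 0.59 with 18 in place of 19 for one covariate.

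**When adjusting loses signal.** Suppose phase moves symptoms only through the marker: within-phase correlation 0.5, marker shift 1.5 SD, hence severity shift 0.5 × 1.5 = 0.75 SD. At an even split, power is roughly 80% unadjusted and roughly 60% adjusted.

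**The case against.** The strongest reply is that the confounding is possible but not shown. Section 1.0 calls the neuropathy often reversible, but only if the taxane is reduced or stopped early enough. It adds that continued treatment raises the risk of irreversible symptoms, that acute symptoms often predict chronic ones, and that some patients develop neuropathy late. Even the direction of a phase effect on severity is therefore open. Section 5.3.2 leaves the serum markers to the investigators, and nothing in the documents says that they change with phase. A reader might infer that corticosteroid premedication suppresses the markers. The documents mention no premedication and no such effect, so that inference is not supported.

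This stands, and it is why the result is stated conditionally and over a range. It does not justify leaving the analysis unadjusted, because the plan also gives no reason to assume that phase is irrelevant.

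Three further points stand in part:
- Section 6.4 sets no threshold, so false-positive rates apply only if 0.05 is used. The shift in the mean correlation needs no threshold.
- The return to 5% after adjustment is partly built in, because the simulation places all confounding in the one binary variable it adjusts for. Timing differences within a phase would remain under a current-versus-previous covariate. Days since last dose deals with more of this, but not with corticosteroid timing.
- Adjustment can remove real signal if the marker lies on the path from treatment to symptoms. This argues against demoting the unadjusted result.

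**Conclusion.** The point holds in conditional form. As planned, a correlation from Section 6.4 describes the pooled sample and cannot be read as a within-phase link. How far it misleads depends on unknowns. Inflation is negligible when both shifts are 0.5 SD (about 6%), material at 1 SD in both (11–15%) and large at 1.5 SD in both (28–44%). Masking is the more sensitive side: opposite shifts of only 0.5 SD lower power from 62% to 43–46%, and opposite 1 SD shifts lower it to 10–15%. The ranges cover 6 and 11 of 22 patients on treatment.

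A reader might go further and infer that a positive result would show only who is still on chemotherapy, or that objective 2.3.2 goes unanswered. The documents do not support either. They do not establish that phase shifts both variables, and the objective is descriptive, so a pooled rank correlation does describe the relation. What it cannot do is separate that relation from phase.

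Only the interpretation of objectives 2.3.1 and 2.3.2 is affected. The primary and secondary conclusions are not.

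**What to change.** In Section 6.4, report a partial Spearman correlation beside the unadjusted one, with a single covariate for treatment phase. Days from last taxane dose to sampling is preferable; current versus previous taxane is the simpler alternative. Derive it from the Appendix D start and stop dates, with the Appendix E blood date for serum markers and the Appendix G biopsy date for mast cells. A patient still on treatment has no final stop date, so state in advance how she is coded, for example as zero days, which ranks her at the on-treatment end.

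Add one sentence on interpretation: a marker–symptom link is described as independent of treatment phase only if it persists after adjustment. Also report how many patients were in each phase.

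The cost is two or three sentences, one degree of freedom, and about two points of power if phase is irrelevant. One covariate is within the limit of two in Section 6.2. The real downside is loss of signal if the marker mediates the phase effect, so both results should be shown and neither demoted. No change to sampling or procedures is needed.
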